## **5- Clinical Implications**

The findings of this study underscore the urgent need to integrate routine psychological screening and targeted psychosocial interventions into oncology care for breast cancer patients in Iraq. The strong associations between stress, sleep disturbances, sedative use, and emotional dysregulation highlight the importance of early detection and management of psychological distress to improve treatment adherence and quality of life. Implementing multidisciplinary care models that include mental health professionals, sleep management programs, and culturally tailored counseling may mitigate the adverse psychological impact observed in advanced-stage patients. These results also suggest the necessity of

training healthcare providers to recognize and address hidden emotional symptoms, thereby promoting holistic cancer care in low-resource settings.

## 6-Conclusion

This study highlights the multifactorial nature of psychological distress among breast cancer patients in Al-Anbar, Iraq. Depression, anxiety, and stress were significantly linked to sleep disruption, sedative use, disease stage, and emotional dysregulation. Advanced cancer stage emerged as a key predictor of heightened anxiety and depression. These findings emphasize the need to integrate psychosocial assessment and targeted interventions into oncological care, particularly in low-resource settings, to mitigate psychological morbidity and improve quality of life in this population.

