## **1-Introduction**

Cancer is one of the most pressing global health concerns. It is stated that there will be four million new breast cancer cases in 2030. World Health Organization (1). Anticipate that cancer numbers will increase significantly, especially in low- and middle-income countries(2). Beyond the physical and financial burdens, cancer is now widely recognized for its profound psychological toll. Emotional distress, such as depression, anxiety, insomnia, and anger, has been identified as a 'silent comorbidity' that can impact treatment adherence, recovery outcomes, and overall quality of cancer patients.

Breast cancer is the most commonly diagnosed cancer among women globally including the Middle East and Iraq. According to the Iraqi Ministry of Health (3). More than 5,000 new breast cancer cases are diagnosed annually, representing over 21% of total new cancer diagnoses in the country(2,3). Unfortunately, due to poor access to screening programs, and limited public awareness, most patients are diagnosed at advanced stages, particularly in underserved regions such as Al-Anbar (4). These patients are at greater risk of experiencing severe psychological consequences due to uncertain prognosis, aggressive treatment protocols, and social isolation (5)

Previous research in Al-Anbar has focused on breast cancer patients (4) Largely focused on pharmacological and economic variables, without exploring behavioral and emotional factors such as sleep quality, emotional regulation (e.g., anger), use of sedatives, or support systems. In the broader Middle Eastern context, recent literature from Jordan, Egypt, and Iran has emphasized the need for Integrated psychosocial evaluation in oncology practice, showing how untreated distress can Exacerbate the overall disease burden (6)(7)(8)(9,10)

A recent study conducted across inpatient and outpatient oncology settings in Jordan reported that 23.4% of cancer patients exhibited depressive symptoms. In comparison, up to 37.6% showed signs of severe anxiety, particularly among inpatients and patients with advanced-stage disease. However, the antidepressant treatment was prescribed for only

15.5% of patients with depression or anxiety (11). These findings highlight A major unmet need in clinical care and reinforce the importance of early screening and targeted psychosocial support in cancer patients.

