### **2-4 Questionnaire tool and data extraction**

Patients' data were collected from medical records (demographics data, medication use history, and clinical profile). Cost data was obtained from the finance department at the center. Financial data included all available direct medical costs, such as treatment and physician visits. Moreover, patients were contacted to estimate the indirect cost associated with breast cancer therapy. A validated assessment tool, the Generalized Anxiety Disorder 7-item (GAD-7) and the Patient Health Questionnaire (PHQ-9) were used to assess anxiety and depression [Spitzer et al., 2006; Kroenke et al., 2001]. The patients were asked to determine the degree of applicability of each item (question) on a 4-point Likert scale. The participants' responses varied from 0 to 3, with 0 denoting "Not at all" and 3 denoting "Nearly every day." Nine elements comprise the PHQ-9 instrument. Items are scored on a scale of 0 to 3, resulting in a total score that ranges from 0 to 27. A total score of 0–4 indicates minimal depression, 5–9 mild depression, 10–14 moderate depression, 15–19 moderately severe depression, and 20–27 severe depression. Seven elements comprise the

GAD-7 instrument. Items are scored on a scale of 0 to 3, resulting in a total score that ranges from 0 to 21. Mild anxiety is indicated by a total score of 5–9, moderate anxiety by 10–14, and severe anxiety by 15–21.

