### 3 - Results

A total of 500 breast cancer patients were included in the final analysis. Descriptive statistics revealed a high prevalence of psychological distress within the sample, with elevated scores in depression, anxiety, and stress domains.

Spearman correlation analysis revealed strong positive associations between sleep difficulty and psychological outcomes: depression ( $r = 0.85$ ), anxiety ( $r = 0.77$ ), and stress ( $r = 0.85$ ), all statistically significant at  $p < 0.001$ . Use of sedatives was also significantly correlated with elevated distress scores ( $r > 0.90$  across models).

Kruskal-Wallis tests demonstrated statistically significant differences in mean ranks of depression, anxiety, and stress across cancer stages ( $p < 0.01$ ), with higher distress in patients with advanced-stage disease.

Multivariate linear regression identified the following as significant predictors of psychological distress:

- PHQ9\_Total:  $\beta = 0.42$ ,  $p < 0.001$
- Anger:  $\beta = 2.08$ ,  $p < 0.001$
- Cancer Stage:  $\beta = 0.92$ ,  $p = 0.0014$

Psychological support was not a significant predictor ( $p = 0.606$ ).

Binary logistic regression showed that PHQ9 and anger significantly predicted severe anxiety, with odds ratios of 1.32 and 1.27, respectively ( $p < 0.001$ ). Stage of disease also emerged as a significant factor in anxiety prediction.

Receiver Operating Characteristic (ROC) curve analysis yielded an Area Under the Curve (AUC) of 0.74 for stress in predicting severe anxiety, indicating a fair level of discriminative ability.

Finally, conceptual path analysis demonstrated that the relationship between stress and anxiety was primarily indirect, mediated through sleep disturbance and daily performance impairment. The direct path from stress to anxiety was negligible ( $r = -0.01$ ), suggesting a mediated mechanism of action.

**Table 1.** Descriptive Statistics of Study Variables

Variable	N	Minimum	Maximum	Mean	SD
Total Cost	500	80	34785	3721.69	4456.79
PHQ9_Total	500	1	27	17.99	6.11
GAD7_Total	500	1	21	12.79	3.81
Cancer Stage	500	0	4	2.52	1.09
Children	500	0	5	2.53	1.63
Metastatic	500	0	1	0.36	0.48
Stress Level	500	0	4	2.64	0.79

The descriptive characteristics of the study variables are presented in **Table 1**. Depression and anxiety scores were moderately high, while stress levels were also elevated. Treatment cost showed substantial variability across participants.

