**Table 5:** Binary Logistic Regression – Predicting Severe Anxiety

Predictor	Odds Ratio (OR)	95% CI	P-value
Depression (PHQ-9)	1.32	1.18 – 1.56	<0.001

Anger	1.27	1.11 – 1.49	0.002
Stress Level	1.14	1.03 – 1.35	0.017
Psychological Support	0.54	0.33 – 0.91	0.021
Cancer Stage	0.61	0.33 – 0.87	0.049

[figure not shown]
Binary logistic regression (**Table 5**) showed that depression, anger, and stress significantly increased the odds of severe anxiety, while psychological support and advanced cancer stage were protective. The corrected model (**Table 6**) confirmed these associations.

**Table 6.** Logistic Regression Predicting Severe Anxiety (Corrected Model)

Predictor	Coef. ( $\beta$ )	Std. Error	z-value	p-value	95% CI (Lower – Upper)
PHQ9_Total	0.42	0.06	6.92	<0.001	0.30 – 0.53
Anger	2.08	0.48	4.36	<0.001	1.14 – 3.02
Psych Support	-0.18	0.34	-0.52	0.606	-0.84 – 0.49
Cancer Stage	0.92	0.29	3.20	0.0014	0.36 – 1.48

[figure not shown]
This table presents the corrected logistic regression model for predicting severe anxiety. PHQ9\_Total and anger were significant positive predictors, while psychological support did not show a significant protective effect in the adjusted model.

**Figure 2.** ROC Curve for stress predicting severe anxiety.

The ROC curve (**Figure 2**) illustrates the predictive value of stress scores for severe anxiety, with an AUC of 0.74 ( $p < 0.001$ ), indicating fair discriminative accuracy.

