Although anger remains an underexplored emotional construct in oncology, its relevance is gaining traction. In Iraq, sociocultural norms that discourage emotional expression, combined with the psychological toll of cancer, may intensify internalized anger, contributing to emotional dysregulation. This perspective is supported by findings from the national report, which highlighted elevated psychological distress among cancer patients and emphasized the role of suppressed emotions in shaping anxiety and avoidance behaviors (20).

These findings emphasize the significance of addressing emotional dysregulation, particularly in patients presenting with overlapping symptoms of depression and anxiety.

This suggests that psychological screening tools should incorporate anger-related items to facilitate the early identification of high-risk cases.

The conceptual path model derived from the dataset suggests that stress influences anxiety primarily through indirect mechanisms, notably sleep disturbance and impaired daily functioning. While the direct association between stress and anxiety was minimal ( $r = -0.01$ ), robust indirect effects were observed via sleep problems ( $r = 0.74$ ) and functional impairment ( $r = 0.77$ ). These findings are consistent with regional studies from Egypt and Oman, highlighting sleep disturbance and fatigue as key mediators of psychological distress in oncology patients. (Al-Habsi et al., 2021; Gabra & Hashem, 2021; Hendy et al., 2025).

This structure reinforces theoretical frameworks such as the Transactional Model of Stress and Coping, where maladaptive emotional responses (e.g., stress) translate into clinical outcomes (e.g., anxiety) through sleep and functional capacity mediators. Similar models have been proposed in Jordanian studies (24). Though the present model uniquely incorporates performance and anger as variables of interest, adding depth to the psychosocial profile.

The inclusion of psychological support and its weak inverse association with anxiety ( $r = -0.07$ ) further suggests that strengthening emotional resources could buffer the transition from stress to anxiety. This model may therefore serve as a foundational structure for targeted interventions in Iraqi cancer care systems, particularly in resource-limited settings.

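### The Conclusion links depression, anxiety and stress to emotional dysregulation, but the readable text and tables report only anger, and only against severe anxiety

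*Combined protocol and SAP*

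**What the plan says.** The Conclusion (section 6) names four factors and ties each to all three outcomes: "Depression, anxiety, and stress were significantly linked to sleep disruption, sedative use, disease stage, and emotional dysregulation". Clinical Implications (section 5) repeats the theme: "The strong associations between stress, sleep disturbances, sedative use, and emotional dysregulation highlight the importance of early detection". The Discussion (section 4) adds: "These findings emphasize the significance of addressing emotional dysregulation, particularly in patients presenting with overlapping symptoms of depression and anxiety".

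On measurement, section 2-4 says that "the Generalized Anxiety Disorder 7-item (GAD-7) and the Patient Health Questionnaire (PHQ-9) were used to assess anxiety and depression". It describes no scale, item or scoring for anger or for emotional dysregulation. The Introduction gives anger as its one example of emotional regulation.

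On results, the text of section 3 says: "Binary logistic regression showed that PHQ9 and anger significantly predicted severe anxiety, with odds ratios of 1.32 and 1.27, respectively". Those odds ratios are in Table 5. Table 6 gives anger a coefficient of 2.08, and the note below it reads: "This table presents the corrected logistic regression model for predicting severe anxiety". Both tables therefore have severe anxiety as their outcome. Section 2-6 sets significance at two-tailed p below 0.05.

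**The concern.** Since section 2-6 defines significance by a test, a significant link to each of three outcomes needs a reported test for each. For emotional dysregulation the reader finds no measure, and for its nearest stand-in, anger, finds tests against one outcome only.

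Two things are at stake. The headline finding, and the clinical message drawn from it, credit depression and stress with an association that no readable result shows. And a single anger variable is presented as a broader construct that the study does not say it measured.

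**Working it through.** **Step 1. Set each factor in the Conclusion against each outcome.**

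| Factor | Depression (PHQ-9) | Anxiety (GAD-7) | Stress |
|---|---|---|---|
| Sleep difficulty (Table 2, Spearman r) | 0.85 | 0.77 | 0.85 |
| Sedative use (Table 4, B) | 4.842, p<0.001 | 4.064, p<0.001 | 1.856, p<0.001 |
| Cancer stage (Table 3, H) | 14.762, p=0.002 | 19.705, p<0.001 | 31.092, p<0.001 |
| Anger (Tables 5 and 6) | none | severe anxiety only: OR 1.27; coefficient 2.08 | none |

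Anger is absent from Tables 1, 2 and 3 and from all three models in Table 4. The other three factors each have some result for every outcome, so the gap is specific to emotional dysregulation. The count of claimed links with a result is anxiety 1, depression 0, stress 0.

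**Step 2. Reproduce the anger row of Table 6** (coefficient 2.08, SE 0.48, z 4.36, CI 1.14 to 3.02).

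- Wald z = coefficient / SE = 2.08 / 0.48 = 4.33. The stated 4.36 is within rounding of the inputs.
- 95% CI = 2.08 ± 1.96 × 0.48 = 1.14 to 3.02, as stated.
- z = 4.36 gives a two-sided p of about 0.000013, consistent with the stated p<0.001.

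**Step 3. Check whether the linear-regression list in section 3 is a separate result.** That list is labelled as predicting psychological distress in general.

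| Term | Linear-regression list | Table 6 (logistic, severe anxiety) |
|---|---|---|
| PHQ-9 | 0.42, p<0.001 | 0.42, p<0.001 |
| Anger | 2.08, p<0.001 | 2.08, p<0.001 |
| Cancer stage | 0.92, p=0.0014 | 0.92, p=0.0014 |
| Psychological support | p=0.606 | p=0.606 |

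Every figure agrees. The Discussion assigns 0.42 and 2.08 to severe anxiety. PHQ-9 is a predictor in this model, so depression cannot be its outcome. The list is Table 6 under another label and adds nothing for depression or stress.

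**Step 4. Put the two anger estimates on one scale.**

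- Table 5: OR 1.27, 95% CI 1.11 to 1.49.
- Table 6: OR = exp(2.08) = 8.0; CI = exp(1.14) to exp(3.02), about 3.1 to 20.5.

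Both show a positive association, but the intervals do not overlap.

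**Step 5. Check the path model.** The Discussion says that it includes anger. The coefficients given in the text are for the direct stress–anxiety path (-0.01), sleep problems (0.74), functional impairment (0.77) and psychological support (-0.07). None is for anger. Figure 3 itself was not available.

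**The case against.** The strongest reply is that the Results do report anger as a significant predictor of distress in general, and that the Discussion speaks of both logistic and linear models. That would cover more than anxiety if it were a separate analysis. The match in step 3 shows that it is not, so this reply fails, but the label invites it and should be corrected.

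A second reply is that Figure 3 may carry an anger path. This stands as a limit: the absence of a depression or stress result is verified only for the readable text and tables. The text describes the figure as a stress–anxiety model, so an anger–stress path is possible; a depression result is less likely.

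A third is that the Discussion calls impaired sleep a possible indicator of emotional dysregulation, so anger need not be the only stand-in. But the Conclusion lists sleep disruption as a separate factor, so sleep cannot also serve as dysregulation there. The Discussion also treats anger as something that contributes to dysregulation, which is not the same as a measure of it.

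A fourth is that section 2-4 describes no instrument for stress, sleep or psychological support either. That is true: the measurement gap is wider than this one construct. Unlike dysregulation, though, stress and sleep at least appear as named variables with results.

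The Clinical Implications sentence is an undifferentiated list and need not be read as a specific stress–dysregulation claim. The Discussion's opening ties emotional regulation only to distress in general, which severe anxiety falls within; there only the label is at issue.

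A reader might infer that anger is unrelated to depression or stress, or that the study holds no such result anywhere. The documents support neither. An unreported association is not an absent one, and Figure 3 has not been seen.

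**Conclusion.** The point holds for the readable text and tables. Of the three links to emotional dysregulation in the Conclusion, one has a reported result, and that result concerns anger and severe anxiety. Depression and stress have no reported coefficient, test or p-value against anger, and no dysregulation measure is described. The one supported link agrees in direction between Tables 5 and 6 but not in size (odds ratio 1.27 against about 8.0).

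This rests on two assumptions: that anger is the variable meant by emotional dysregulation, as the Introduction's example suggests, and that the linear-regression list duplicates Table 6, as the identical figures indicate. An anger path in Figure 3 could change the count for stress. The data are not called into question; the wording of a headline conclusion goes beyond what is shown.

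**What to change.** Choose one of two routes for Clinical Implications and the Conclusion:

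- Analyse anger against PHQ-9 and against stress in the existing data, or cite Figure 3 if it shows such a path, and keep only the links that the results support.
- Otherwise, limit both sections to an association between anger and severe anxiety (GAD-7 of 15 to 21 in section 2-4).

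On either route:

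- Use the word anger for the study's own result in the Discussion, Clinical Implications and Conclusion. The Discussion's opening sentence needs only this change of term.
- Relabel the linear-regression list in section 3 as the Table 6 logistic model for severe anxiety.
- Reconcile the anger estimates in Tables 5 and 6 before the association is stated in the Conclusion.

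The cost is rewording in four sections, a check of two fitted models and, on the first route, two further analyses of data already held. The downside is a narrower headline claim.

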**Table 2.** Spearman Correlation Matrix Among Study Variables

Variable	PHQ9_Total	GAD7_Total	Stress Level	Sleep Difficulty	Sleep Satisfaction	Total Cost

PHQ9_Total	1.00	0.79	0.66	0.85	0.49	-0.11
GAD7_Total	0.79	1.00	0.65	0.77	0.62	-0.10
Stress Level	0.66	0.65	1.00	0.85	0.55	-0.12
Sleep Difficulty	0.85	0.77	0.85	1.00	0.48	-0.08
Sleep Satisfaction	0.49	0.62	0.55	0.48	1.00	-0.09
Total Cost	-0.11	-0.10	-0.12	-0.08	-0.09	1.00

[figure not shown]
Spearman correlation coefficients between psychological outcomes and sleep-related variables are shown in **Table 2**. Strong positive correlations were observed between depression, anxiety, stress, and sleep difficulty.

**Table 3.** Kruskal–Wallis Test for Differences Across Cancer Stages

Variable	Chi-square (H)	df	P-value
Stress Level	31.092	3	<0.001
PHQ9_Total	14.762	3	0.002
GAD7_Total	19.705	3	<0.001

The Kruskal–Wallis test results (**Table 3**) indicate significant differences in depression, anxiety, and stress levels across cancer stages ( $P < 0.05$ ).

**Figure 1.** Chi-square (H) Values for Stress, Depression, and Anxiety

**Figure 1** shows the Chi-square (H) values for stress, depression, and anxiety. Stress exhibited the highest value (H = 31.09), followed by anxiety (H = 19.71) and depression (H = 14.76), all indicating significant differences across groups ( $P < 0.05$ ).

**Table 4.** Multiple Regression Analysis of Factors Associated with Depression, Anxiety, and Stress among Patients

Outcome	Predictor	B	T	P-value	VIF	R 
Depression (PHQ-9)	Use of Sedatives	4.842	10.817	<0.001	1.766	0.702
	Sleep Difficulty	4.52	11.221	<0.001	4.866	
	Sleep Satisfaction	0.364	2.01	0.045	1.021	
	Children	0.075	0.626	0.532	1.039	
	Total Cost	7.5E-5	2.209	0.028	1.022	

	Metastatic	-0.13	-0.408	0.684	1.048	
Anxiety (GAD7)	Use of Sedatives	4.064	12.807	<0.001	1.766	0.615
	Sleep-related Worry	1.521	6.193	<0.001	3.655	
	Sleep Satisfaction	0.539	1.886	0.060	4.866	
	Children	0.205	1.889	0.060	1.039	
	Total Cost	3.0E-5	1.246	0.213	1.022	
	Metastatic	0.203	0.896	0.371	1.048	
Stress Level	Use of Sedatives	1.856	29.413	<0.001	1.766	—
	Sleep-related Worry	0.149	3.048	0.002	3.655	
	Children	0.037	1.705	0.089	1.039	
	Metastatic	0.084	1.865	0.063	1.048	
	Total Cost	3.4E-6	0.711	0.477	1.022	

The results of the multiple regression analysis are summarized in **Table 4**. Use of sedatives and sleep-related worry were significant predictors of stress, depression, and anxiety scores.

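### The adjusted evidence on cancer stage is logistic output labelled as linear regression, a contradictory Table 5 is still reported beside the corrected Table 6, and for depression the stage test is unadjusted only

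*Combined protocol and SAP*

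**What the plan says.** The document reports a completed cross-sectional study of 500 patients. Section 2-6 plans two separate regressions: linear models for PHQ-9, GAD-7 and stress, and a binary logistic model for severe anxiety.

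- **Section 3, text.** "Multivariate linear regression identified the following as significant predictors of psychological distress": PHQ-9 0.42, anger 2.08, cancer stage 0.92 (p = 0.0014), with psychological support not significant (p = 0.606). Then: "Binary logistic regression showed that PHQ9 and anger significantly predicted severe anxiety, with odds ratios of 1.32 and 1.27, respectively", both with p < 0.001, and "Stage of disease also emerged as a significant factor in anxiety prediction", with no odds ratio or direction.
- **Table 3.** Kruskal-Wallis tests with 3 df are said to "indicate significant differences in depression, anxiety, and stress levels across cancer stages".
- **Table 5** (logistic, severe anxiety). Stage has OR 0.61 (0.33 to 0.87, p = 0.049). The text says depression, anger and stress raise the odds, "while psychological support and advanced cancer stage were protective", and that Table 6 "confirmed these associations".
- **Table 6** (logistic, severe anxiety). "This table presents the corrected logistic regression model for predicting severe anxiety". Stage has a coefficient of +0.92, and support has p = 0.606.
- **Section 4.** The 0.92 is described as predicting higher anxiety scores once stage coding was adjusted. The values 0.42 and 2.08 are credited to logistic and linear models alike. Support is given OR 0.54, with p = 0.606 in the adjusted model.
- **Section 6.** "Advanced cancer stage emerged as a key predictor of heightened anxiety and depression".

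**The concern.** Stage is one of the study's headline findings and the basis for the call in Section 4 for stage-specific interventions. Three things undermine it as printed.

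First, log-odds presented as linear coefficients invite the reader to take 0.92 as a change in score. They also suggest that two kinds of model agree, when the figures come from one.

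Second, the Results call advanced stage protective in one place, while the Discussion and Conclusion say the opposite. A reader cannot tell which model the authors stand behind, because results from both are cited as findings.

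Third, and less serious, the Conclusion treats anxiety and depression alike, although depression has no adjusted analysis by stage.

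**Working it through.** **1. Source of the values called linear.** The Results text gives 0.42, 2.08, 0.92, p = 0.0014 and p = 0.606. All five appear in Table 6, which is logistic and prints z-values. In Table 4 the predictors are sedative use, sleep items, children, cost and metastatic status. Stage, anger, psychological support and PHQ-9 are not predictors in any of its three models.

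**2. Does Table 6 agree with itself?** With z = coefficient / SE and OR = exp(coefficient):

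| Row | Coef. / SE | z computed | z printed | OR (95% CI) |
|---|---|---|---|---|
| PHQ-9 | 0.42 / 0.06 | 7.00 | 6.92 | 1.52 (1.35 to 1.70) |
| Anger | 2.08 / 0.48 | 4.33 | 4.36 | 8.00 (3.13 to 20.5) |
| Support | -0.18 / 0.34 | -0.53 | -0.52 | 0.84 (0.43 to 1.63) |
| Stage | 0.92 / 0.29 | 3.17 | 3.20 | 2.51 (1.43 to 4.39) |

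All rows agree within the rounding of the SE. The stage z of 3.20 gives p = 0.0014, as printed.

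**3. Table 5 against Table 6.**

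| Predictor | Table 5 OR (p) | Table 6 OR (p) |
|---|---|---|
| Stage | 0.61 (0.049) | 2.51 (0.0014) |
| Support | 0.54 (0.021) | 0.84 (0.606) |
| Anger | 1.27 (0.002) | 8.00 (<0.001) |
| PHQ-9 | 1.32 (<0.001) | 1.52 (<0.001) |
| Stress | 1.14 (0.017) | not in model |

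For stage, the log-odds differ by 0.92 - ln(0.61) = 1.41, a 4.1-fold ratio of odds ratios, and the two intervals lie on opposite sides of 1. Stage reverses and support loses significance, so Table 6 does not confirm Table 5.

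**4. Can stage coding explain the change?** Reversing Table 5's stage scale gives 1 / 0.61 = 1.64 (1.15 to 3.03), not 2.51, and a pure reversal would leave every other coefficient unchanged. Anger's scale is undefined, so part of its shift may be units. A change of units leaves z unchanged, however, and anger's z goes from about 3.1 (from p = 0.002) to 4.36. Dropping stress or regrouping stage may contribute. The document does not say.

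**5. Does Table 5 agree with itself?** These checks assume Wald intervals; Section 2-6 does not name the method.

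- *Stage.* The interval 0.33 to 0.87 centres on sqrt(0.33 × 0.87) = 0.54, with SE = ln(0.87 / 0.33) / 3.92 = 0.247. Around its own centre this gives p = 0.012. Conversely, OR 0.61 with p = 0.049 (z = 1.969) gives SE = 0.251 and an interval of 0.37 to 1.00. The interval width fits the p-value when centred on 0.61 (p = 0.046), so the mismatch is mainly one of location.
- *Stress.* The interval 1.03 to 1.35 centres on 1.18 and gives p = 0.017, as printed. Interval and p-value agree, so the OR of 1.14 is the odd figure. With p = 0.017 it would imply 1.02 to 1.27.

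**6. Mixed citations in the text.** The Results give anger the Table 5 OR of 1.27 with p < 0.001, but Table 5 prints p = 0.002. The Discussion pairs Table 5's support OR of 0.54 with Table 6's p = 0.606; Table 6's own OR is 0.84.

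**7. Stage and depression.** The Kruskal-Wallis p-values reproduce at 3 df: PHQ-9 H = 14.762, p = 0.0020; GAD-7 H = 19.705, p = 0.0002. H / (N - 1) = 14.762 / 499 = 0.030, so stage accounts for about 3% of the rank variance of PHQ-9. The test is omnibus and unadjusted, and no by-stage values are shown. Table 6 uses PHQ-9 as a predictor, so it says nothing about depression as an outcome. The nearest adjusted term in Table 4, metastatic status, has B = -0.13 for PHQ-9; SE = 0.13 / 0.408 = 0.319, 95% CI -0.75 to 0.49, p = 0.684. It is not the same variable as stage, but it lends no support. Table 1 ranges stage from 0 to 4 while 3 df means four groups. With 4 df the p-values would be 0.0052 and 0.0006, so significance does not depend on this.

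**The case against.** The best defence is that the label of Table 6 retires Table 5. The direction of stage in the Discussion and Conclusion follows Table 6, which is internally consistent and correctly titled as logistic. The loss of significance for support is disclosed in the Results, in the note to Table 6 and in the Discussion. The Discussion mentions stage coding as the reason for a change. The Results list names only psychological distress as its outcome, so not every reader would take 0.92 as GAD-7 points. Figure 3 is said to carry further coefficients and is not visible to us. The arithmetic faults in Table 5 become moot if that table is withdrawn.

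Much of this is fair. Table 6 probably does supersede Table 5, and the disclosure on support is real. But the text still presents Table 5's odds ratios and its protective reading of stage as findings, and says the corrected model confirms them. Figure 3 is unlikely to supply the missing linear model, because the quoted values match Table 6 exactly. The Discussion's wording about anxiety scores, and its appeal to two model types, still lack support in Table 4.

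**Conclusion.** The concern holds and needs correction before the stage conclusion can be used. The mislabelling and the contradiction between Tables 5 and 6 follow from comparing printed figures and need no assumption. If Table 6 is the valid model, the adjusted evidence is OR 2.51 (1.43 to 4.39) for severe anxiety per unit of stage as coded. That coding is not described; if stage was grouped into two, 2.51 is a group contrast. There is no printed adjusted evidence that stage predicts GAD-7 scores or depression.

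The unadjusted Kruskal-Wallis results stand for both outcomes, so the correction narrows the stage claim and does not remove it. The wording on depression is a minor point; the mislabelling and the two conflicting models determine the seriousness.

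**What to change.** 1. Check the software output and relabel the coefficients in the Section 3 list as logistic log-odds for severe anxiety, preferably shown as odds ratios.
2. In Section 4, correct the statement that stage predicted anxiety scores and the statement that logistic and linear models agree on PHQ-9 and anger.
3. Keep one severe-anxiety model. If it is Table 6, delete Table 5, the protective reading of stage and support, the claim of confirmation, and the odds ratios 1.32, 1.27 and 0.54 wherever they are cited. State how stage and anger were coded and why stress was left out.
4. Add PHQ-9 and GAD-7 medians or mean ranks by stage, grouped as in Table 3, and state how stages 0 to 4 became four groups.
5. In Section 6, limit the adjusted stage claim to severe anxiety and call the depression link an unadjusted association. Linear models with stage as a predictor are needed only if the authors want an adjusted claim for depression or GAD-7 scores.

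The cost is a check of existing output, text edits and one descriptive table, with no new data. The price is a narrower conclusion on stage.
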